## 7. Study Discontinuation and Withdrawal

All subjects have the right to withdraw at any point during treatment without prejudice. If for any subject, study treatment or observations were discontinued, the reason(s) will be recorded and the sponsor will be notified promptly. Reasons that a subject may discontinue participation in a clinical study include:

- Subject withdrew consent
- Subject chooses to withdraw due to an adverse experience
- Lost to follow-up (LTFU)

Before a subject is identified as LTFU, the site will make all reasonable efforts to contact the subject. **These attempts will be documented and will include, at a minimum two phone calls and/or email communications and one follow-up letter sent via certified mail.**

The investigator may discontinue a subject at any time if it is considered medically necessary. Rationale for discontinuation of a subject for medical reasons include, but are not limited to, the following:

- Repeat infections with no response to allowable treatments
- Subject repeated non-compliance with randomized treatment
- It is in the best interest of the subject to not participate in the study.
- Medical reason or situation in which the subject is no longer under the care of the investigator and unable to return for required study visits (e.g., hospitalization).

Every attempt should be made to collect follow-up information. The reason for treatment discontinuation or withdrawal from the study will be recorded in the source documents and on the appropriate eCRF.

The subject may be discontinued by the sponsor if the study is discontinued or for lack of compliance/protocol deviations.

All subjects choosing to withdraw from the study will be asked to undergo the appropriate study visit procedures for the visit at which they are withdrawing. All subjects being discontinued by either the investigator or the sponsor will undergo the appropriate study visit procedures for the visit at which the decision is made to withdraw them from the study.

Subjects who are discontinued or withdrawn and who have not achieved 100% ulcer closure during the treatment phase of the study will not be replaced and will be categorized as treatment failures.

## 8. Statistical Analysis

This Section presents general information about statistical methodologies and concepts for this study. Further technical details (e.g., data poolability across sites) will be provided in the Statistical Analysis Plan (SAP).

## 8.1. Treatment Groups

The following treatment groups will be assessed:

Group	Description
Control (SOC)	Moist ulcer dressings consisting of 0.9% sodium chloride gel plus secondary dressings and an appropriate off-loading/protective device. (See Section 5.11 for full information)
Active Treatment	PriMatrix Dermal Repair Scaffold plus secondary dressings to maintain a moist wound healing environment and an appropriate off-loading/protective device. (See Section 5.17 for full information)

## 8.2. Description of Study Endpoints

### 8.2.1. Primary Efficacy Endpoint

The primary efficacy endpoint for the study is the incidence of confirmed complete wound closure of the study ulcer, as assessed by the investigator, during the 12-week treatment phase.

### 8.2.2. Secondary Efficacy Endpoints

The secondary endpoints are:

1. Proportion of subjects with complete wound closure of the study ulcer during the 12-week treatment phase as assessed by computerized planimetry, during the treatment phase
2. Time to complete wound closure, as assessed by the investigator.
3. Time to complete wound closure, as assessed by computerized planimetry.
4. Rate of ulcer closure as assessed by computerized planimetry.

### 8.2.3. Exploratory Endpoints

9. Medical resource utilization associated with treatment of DFU and related complications, including:
  - Interference of activities of daily living
  - Interference of paid work (full-time or part-time)/school
  - Physician office visits
  - Emergency room visits
  - Hospitalizations
  - Home health nursing visits
  - Skilled Nursing Facilities
  - Procedures
  - Medication regimens to treat complications (analgesics, antibiotics, etc.)

- Diagnostic tests, imaging, etc.
- Treatment of AEs
- Use of durable medical equipment (off-loading/protective device, crutches, wheelchair, etc.)
- Dressing regimen and materials

10. Wound closure status at the 4-week follow-up visit

#### 8.2.4. Safety Endpoints

Safety will be assessed through reports of AEs and SAEs.

#### 8.3. Sample Size Determination and Rationale

This is a randomized study with two treatment groups. Assuming:

- 46% of DFUs receiving PriMatrix close by 12 weeks (84 days).
- 26% of DFUs receiving with SOC close by 12 weeks (84 days).

Overall 2-sided Type I Error rate (alpha) of 0.05. Under the above assumptions, 102 subjects per treatment group will be required to meet the Type I error rate of 0.05 and 80% power; for a total of 204 subjects for the study. As the treatment duration is short, the discontinuation rate is predicted to be around 15%. To accommodate the potential discontinuations, 256 subjects will be randomized (128 per treatment group) to this trial. The subjects will be randomized to the treatment groups in a 1:1 ratio.

A single interim analysis when 50% of subjects complete the trial, using group-sequential methods and Pocock alpha spending function, where the hypotheses will be tested at a two-sided alpha of 0.031 at the interim analysis and at a two-sided alpha of 0.028 at the final analysis.

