## 3. Study Design

This is a multicenter, randomized, open-label, parallel-group clinical trial designed to establish the superior efficacy of PriMatrix over that of Control treatment in the management of DFUs in subjects with DM and adequate arterial circulation. Study enrollment will be paused once 50 subjects (25 in each treatment arm) have been enrolled in order to do an early data review. There will also be an interim analysis after 128 subjects have completed their study requirements.

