2. INTRODUCTION

This document provides a detailed description of the statistical methods and procedures to be implemented during the analysis of the clinical study. The methods and procedures are intended to support the generation of study report, including detailed descriptions of the populations and methodologies, as well as summary tables, listings and graphics.

This statistical analysis plan (SAP) is based on Version 5.0 of the Protocol # T-PMXDFU-01.

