4. STUDY DESIGN

This is a multicenter, randomized, open-label, parallel-group clinical trial designed to establish the superior efficacy of PriMatrix over that of Control treatment in the management of DFUs in subjects with DM and adequate arterial circulation. Study enrollment will be paused once 50 subjects (25 in each treatment arm) have been enrolled in order to do an early data review. There will also be an interim analysis after 120 subjects have completed their study requirements.

Treatment Groups

- Active Treatment – PriMatrix Dermal Repair Scaffold + SoC
- Control Treatment – SoC

Study Phases

- **Screening Phase**

After the informed consent process is complete, medical history will be collected and clinical assessments will be performed to determine subject eligibility for the study. If the required eligibility criteria are met, the subject will begin the two-week screening phase. During this phase, the subject will receive the control treatment as defined in Section 5. During the two-week screening phase, the investigator will determine if the subject continues to meet all eligibility criteria, and if confirmed, the subject will be randomized and enter the treatment phase.

- **Treatment Phase**

Subjects will be randomized to receive the Active or Control Treatment in a 1:1 scenario (details can be found in Section 8.4). Efficacy evaluations during this phase include weekly investigator assessments of wound closure and planimetric evaluations of ulcer area. Safety evaluations will include AE assessments at each visit. Additionally, collection of medical resource utilization (MRU) data will occur. The randomized study treatment will be administered for up to 12 weeks or until the study ulcer has closed, as assessed by the investigator.

At the end of the treatment phase, subjects, all of whom will be considered treatment phase completers, will be assigned to one of two outcomes:

- Subjects with confirmed closed ulcers will be considered treatment successes.
- Subjects with open ulcers at the end of the treatment phase will be considered treatment failures.

Unscheduled Visits (i.e., those not specifically scheduled per protocol) are at the discretion of the investigator. If the unscheduled visit is for treatment of the target ulcer, data for that visit will be collected and reported on the Unscheduled Visit eCRF page. For detailed information, see Figure 1 and Table 3 below.

[figure not shown]
- **Follow-up Phase**

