6. SAMPLE SIZE DETERMINATION AND RATIONALE

This is a randomized study with two treatment groups. Assuming:

- 46% of DFUs receiving PriMatrix close by 12 weeks (84 days).
- 26% of DFUs receiving with Standard of Care close by 12 weeks (84 days).

Overall 2-sided Type I Error rate (alpha) of 0.05. Under the above assumptions, 102 subjects per treatment group will be required to meet the Type I error rate of 0.05 and 80% power; for a total

of 204 subjects for the study. As the treatment duration is short, the discontinuation rate is predicted to be around 15%. To accommodate the potential discontinuations, 240 subjects will be randomized (120 per treatment group) to this trial. The subjects will be randomized to the treatment groups in a 1:1 ratio.

A single interim analysis when 50% of subjects complete the trial, using group-sequential methods and Pocock alpha spending function, where the hypotheses will be tested at a two-sided alpha of 0.031 at the interim analysis and at a two-sided alpha of 0.028 at the final analysis.

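### Protocol 5.0 randomises 256 with an interim at 128, but its own 204 and 15% give 240; the SAP uses 240 and 120 without recording the change

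*Protocol*

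**What the plan says.** Both documents start from the same design: closure of 46% against 26% by 12 weeks, two-sided alpha of 0.05 overall, 80% power, 102 subjects per arm (204 in total), and discontinuation of around 15%. They then part.

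- **Randomised total.** Protocol 8.3: "256 subjects will be randomized (128 per treatment group) to this trial". The protocol synopsis also gives 256. SAP 6: "240 subjects will be randomized (120 per treatment group) to this trial". SAP 10.4 treats 240 as full enrolment.
- **Interim trigger.** Protocol 3: "There will also be an interim analysis after 128 subjects have completed their study requirements", and the synopsis agrees. SAP 4: "There will also be an interim analysis after 120 subjects have completed their study requirements".
- **Link between the two.** SAP 2: "This statistical analysis plan (SAP) is based on Version 5.0 of the Protocol". Version 05 is the protocol supplied here, so the SAP cites the document whose figures it does not follow.

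The SAP change history from version 1.0 to 1.1 lists its corrections. Neither 256 to 240 nor 128 to 120 is among them.

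Both documents also describe the interim as falling when 50% of subjects complete, with two-sided levels of 0.031 at the interim and 0.028 at the end.

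**The concern.** There are two faults. First, the protocol's randomised total does not follow from the inputs in the same paragraph. Second, two current documents give different values for the enrolment target and for the number of completers that triggers the only efficacy look.

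The interim count is not a clerical detail in an open-label trial with a stopping rule. A reader of the final report should be able to confirm that the look was taken at the pre-specified point. With 120 in one document and 128 in the other, a look at either number agrees with one document and departs from the other. The planned total is also the denominator of the information fraction in the conditional-power formula of SAP 9.2. It is the benchmark, too, against which SAP 10.4 reports that enrolment stopped early.

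**Working it through.** **Inputs.** From Protocol 8.3 and SAP 6: p1 = 0.46, p2 = 0.26, 102 per arm, 204 in total, loss d = 0.15, interim and final two-sided levels 0.031 and 0.028 at 50% information. From Protocol 8.6 and SAP 9.1: early-stopping probability 0.479. From SAP 11.1.1: 207 patients in the primary efficacy population.

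**Step 1: reproduce the evaluable number.** The mean proportion is 0.36. With pooled variance, the expected Z at n per arm is 0.20 / √(2 × 0.36 × 0.64 / n).

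- Interim, n = 51 per arm: expected Z = 2.104. The critical value for 0.031 is 2.157. P(stop for superiority) = 1 − Φ(2.157 − 2.104) = 0.479, the stated figure.
- Both looks together, n = 102 per arm, correlation √0.5: power = 0.803. The requirement for 80% is 101.3, rounded up to 102.

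So 102 per arm and 204 in total are right. The 0.479 was evidently computed on the 204, so it does not show which randomised total was intended.

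**Step 2: the inflation for loss.**

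- N/(1 − d): 204/0.85 = 240; per arm 102/0.85 = 120.
- The cruder N × (1 + d): 204 × 1.15 = 234.6, or 235; per arm 117.3, or 118 (236 in total).

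No variant at 15% gives 256. In reverse, 1 − 204/256 = 0.203, a loss of 20.3%. At 15% loss, 256 × 0.85 = 217.6 remain evaluable and 240 × 0.85 = 204. The SAP's figure fits the shared inputs and the protocol's does not. The gap is 16 subjects, 16/240 = 6.7%.

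**Step 3: effect on the type I error rate.** Overall alpha = 1 − P(|Z1| < 2.157 and |Z2| < 2.197), with correlation √t, where t is the information fraction.

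| Interim / total | t | Overall two-sided alpha |
|---|---|---|
| 128/256 (protocol) | 0.500 | 0.0502 |
| 120/240 (SAP) | 0.500 | 0.0502 |
| 120/256 (mixed) | 0.469 | 0.0508 |
| 128/240 (mixed) | 0.533 | 0.0495 |
| 120/207 (assuming a look at 120) | 0.580 | 0.0486 |
| 128/207 (assuming a look at 128) | 0.618 | 0.0477 |

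The excess of 0.0002 at exactly 50% comes from rounding the two levels to three decimals. The worst mixture adds 0.0006 to that. The last two rows are illustrations only, since neither document reports the count at which the interim was taken.

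**The case against.** The strongest reply is that nothing of inferential weight turns on this, and much of it stands.

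- Read alone, each document is coherent about timing: 128 is half of 256 and 120 is half of 240. Both state the same 50% rule and the same levels. The mixed fractions in the table belong to neither plan.
- A reader might infer that the mismatch inflates the type I error rate. The documents do not support that. The largest value is 0.0508 against a baseline of 0.0502, and the other mixture falls below 0.05. The plan also names a Pocock spending function, under which levels can be recomputed at the observed information.
- A reader might infer that the trial was under-sized. The protocol's slip runs the other way, with about 218 evaluable at 15% loss against 204 needed.
- The enrolment target has been overtaken. SAP 10.4 says enrolment ended before 240, and SAP 11.1.1 fixes the primary set at 207. Neither planned total is the denominator of the final analysis.
- The protocol hedges: the synopsis speaks of up to 256, and the loss rate is only approximate.

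The last point does not rescue the figure. Protocol 8.3 gives 256 as the number to be randomised, an approximate 15% does not reach 20.3%, and a ceiling on enrolment does not explain two interim counts. That enrolment has stopped changes the remedy but leaves the discrepancy in place: the interim rule still needs one pre-specified count.

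**Conclusion.** The point holds as an arithmetic error in Protocol 8.3 and an unrecorded conflict between protocol and SAP. The inputs support 240 with the interim at 120. The protocol exceeds these by 16 subjects and 8 completers. Planned power is not reduced, and the effect on overall alpha is negligible (0.0495 to 0.0508 across the mixed readings, against 0.0502). The consequence is that the planned total and the pre-specified interim count cannot be verified from the documents.

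This rests on the usual inflation N/(1 − d), on information proportional to the number of subjects, and on the stated levels being used unchanged.

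Two further inferences should be resisted. The number 256 matches a 20% loss rounded up per arm (102/0.80 = 127.5, hence 128), so a leftover 20% assumption is plausible, but neither document says so. Nor do the documents show that the interim was taken at the wrong time, since they do not give the count used.

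**What to change.** 1. Take 240 randomised (120 per arm) and an interim after 120 completers as the planned figures, since they follow from 204 and 15%. Correct the 256 and 128 in the protocol synopsis, section 3 and section 8.3 accordingly, as a correction for the record.
2. In SAP 4, 6 and 9, state that 240 and 120 depart from Protocol 5.0, which has 256 and 128, and give the reason. Add a line to the change history.
3. Record in the SAP and the study report the count at which the interim was actually taken. Report its information fraction against the final analysed number (207 in SAP 11.1.1) as well as against the planned total.
4. Leave the 15% assumption as it is. Restating it as 20% now would supply a rationale after enrolment had ended.

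The cost is a few sentences, mainly in the SAP. No data collection, analysis method or significance level changes.

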#### 8.4. Randomization

The randomization will be stratified by center and will use mixed blocks of 2 and 4 with a 1:1 ratio of Active Treatment to Control Treatment to ensure even distribution of Active and Control subjects at each site. Trial ulcer size (area) at the time of randomization (2 strata: 1 cm^2 to ≤3 cm^2 vs. >3 cm^2 to 12 cm^2) will also be used as a stratification factor to ensure balance between each treatment group in this stratum.

#### 8.5. Blinding

Due to the nature of this trial and the product, the subjects, investigators and personnel involved in this trial cannot be blinded. The assessment of ulcer closure, determination of ulcer area and ulcer closure parameters will be determined by both the investigator and by computerized planimetric analysis of digital photographs of the DFU using an imaging system and associated software.

## 8.6. Interim Analysis for Sample Size Adjustment

A single interim analysis will be completed when 50% of subjects complete the study. Employing a group-sequential design with a Pocock alpha spending function the following decisions will be made at the interim analysis with respect to the efficacy outcome:

1. Stop the study due to demonstrating statistically significant superiority of the Active Treatment to SOC if the two-sided p-value testing the stated hypotheses is  $\leq 0.031$  and the difference is in favor of the Active Treatment.
2. Stop the study due to demonstrating futility of the Active Treatment to SOC if the two-sided p-value testing the stated hypotheses is  $\leq 0.031$  and the difference is in favor of SOC.
3. Continue the study if the two-sided p-value testing the stated hypotheses is  $> 0.031$ .

With this design and assuming 46% of DFUs managed with the Active Treatment achieve complete wound closure by Week 12 (or by TV13) and 26% achieve complete wound closure when managed with the Control Treatment, the probability of stopping early due to showing superiority with the Active Treatment is 0.479. If the decision at the interim analysis is to continue the study, the hypotheses at the end of the study will be tested at a two-sided alpha level of 0.028 to maintain an overall two-sided alpha of 0.05.

Further, conditional power will be calculated at the interim analysis for predicting the final study success. In case more data is needed, sample size re-estimation will be considered in order to meet the final study objective.

In addition, an early data review will be performed when 50 patients reach the primary endpoint. The purpose of this review is to ensure the study execution is as originally planned, and therefore, no alpha spending is involved.

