9. INTERIM ANALYSIS FOR SAMPLE SIZE ADJUSTMENT

9.1. Interim Prediction for Early Success

A single interim analysis will be performed when 50% of subjects complete the study. By employing a group-sequential design with a Pocock alpha spending function, the following decisions will be made at the interim analysis with respect to the efficacy outcome:

- 1) Stop the study upon demonstrating statistically significant superiority of the Active Treatment (PriMatrix Dermal Repair Scaffold) to the Control Treatment (Standard of Care) if the two-sided p-value testing the stated hypotheses is ≤ 0.031 and the difference is in favor of the Active Treatment (PriMatrix Dermal Repair Scaffold).
- 2) Stop the study upon demonstrating futility of the Active Treatment (PriMatrix Dermal Repair Scaffold) to the Control treatment (Standard of Care) if the two-sided p-value

testing the stated hypotheses is ≤ 0.031 and the difference is in favor of the Control Treatment (Standard of Care).

- 3) Continue the study if the two-sided p-value testing the stated hypotheses is > 0.031 .

With this design and assuming 46% of DFUs managed with the Active Treatment achieve complete wound closure by 12 weeks and 26% achieve complete wound closure when managed with the Control Treatment, the probability of stopping early due to showing superiority with the Active Treatment (PriMatrix Dermal Repair Scaffold) is 0.479. If the decision at the interim analysis is to continue the study, the hypotheses at the end of the study will be tested at a two-sided alpha level of 0.028 to maintain an overall two-sided alpha of 0.05.

Further, conditional power will be calculated at the interim analysis for predicting the final study success. In case more data is needed, sample size re-estimation will be considered in order to meet the final study objective.

Conditional Power

Conditional power: the probability of statistical significance at the completion of the study given the data obtained so far. From Jennison and Turnbull (2000) pages 205 to 208, the general upper one-sided conditional power at stage k for rejecting a null hypothesis about a parameter θ at the end of the study, given the observed test statistic, Z_k , is computed as

$$P_{uk}(\theta) = \Phi\left(\frac{Z_k \sqrt{I_k} - z_{1-\alpha} \sqrt{I_K} + \theta(I_K - I_k)}{\sqrt{I_K - I_k}}\right),$$

the general lower one-sided conditional power at stage k is computed as

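### The stated 0.479 chance of stopping early for superiority belongs to a 102-subject interim, not the 128 or 120 completed subjects the documents specify

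*Protocol*

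**What the plan says.** Protocol Section 8.6 gives the operating characteristic of the single efficacy look: under 46% closure on PriMatrix and 26% on standard of care, "the probability of stopping early due to showing superiority with the Active Treatment is 0.479". The protocol synopsis gives the same value, and so does SAP Section 9.1 ("is 0.479. If the decision at the interim analysis is to continue the study").

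The two documents set the size of that look differently:

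- Protocol Section 3 (and the synopsis): "There will also be an interim analysis after 128 subjects have completed their study requirements".
- SAP Section 4: "There will also be an interim analysis after 120 subjects have completed their study requirements".

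Both also place the look at the point where 50% of subjects have completed, without saying 50% of what. Three totals are available: 204 (needed for 80% power, in both documents), 256 (randomised, Protocol Section 8.3) and 240 (randomised, SAP Section 6). The stated counts of 128 and 120 are half of 256 and half of 240.

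Protocol Section 8.3 says the hypotheses are "tested at a two-sided alpha of 0.031 at the interim analysis and at a two-sided alpha of 0.028 at the final analysis".

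**The concern.** With the closure rates, allocation and boundary fixed, the chance of crossing the boundary depends only on the number of subjects at the look. The protocol and SAP use different numbers and report the same probability to three decimals, so at least one must be wrong.

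This probability is the only quantitative description of how the interim is expected to behave. If it was computed for a smaller look than the one specified, anyone using it to plan for an early stop is using the wrong figure. The mismatch also shows that the base for the 50% is unsettled. That matters beyond this one number, because the 0.031 level assumes that the look falls at half of the final information.

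**Working it through.** **Inputs.** Closure rates 0.46 and 0.26, 1:1 allocation, 102 per arm for 80% power, overall two-sided alpha 0.05, and nominal levels 0.031 and 0.028 (Protocol Section 8.3). Stop for superiority if two-sided p ≤ 0.031 in favour of PriMatrix (Protocol Section 8.6). Interim at 128 completed subjects, 64 per arm (Protocol Section 3), or 120, 60 per arm (SAP Section 4).

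**Formula.** The critical value for two-sided 0.031 is z = 2.157. The mean closure rate is (0.46 + 0.26)/2 = 0.36, so with n per arm

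SE = √(2 × 0.36 × 0.64 / n) = √(0.4608 / n)

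P(stop for superiority) = Φ(0.20/SE − 2.157)

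**Step 1: reproduce the plan's figure.** At n = 51, SE = 0.0951 and the drift is 0.20/0.0951 = 2.104. Then Φ(2.104 − 2.157) = 0.479, which matches. A version using the null variance for the boundary and the alternative variance for the spread gives 0.478.

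**Step 2: check that 51 per arm belongs to the rest of the design.** The Pocock-type spending function at half information gives 0.05 × ln(1 + (e − 1) × 0.5) = 0.0310. The matching final level is 0.0277, stated as 0.028. Two-stage power at 102 per arm is 0.803. The stated levels, the 80% power and the 0.479 therefore all come from a 204-subject design with its look at 102.

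**Step 3: same formula at the stated interim sizes.**

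| Interim total | Per arm | Drift | P(stop for superiority) | Minus 0.479 |
|---|---|---|---|---|
| 102 | 51 | 2.104 | 0.479 | 0.000 |
| 120 (SAP) | 60 | 2.282 | 0.550 | +0.071 |
| 128 (Protocol) | 64 | 2.357 | 0.579 | +0.100 |

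**Step 4: sensitivity to the form of the test.** Across uncorrected variants (pooled, unpooled and exact enumeration), the range is 0.550 to 0.574 at 120 and 0.579 to 0.604 at 128. None comes near 0.479.

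**Step 5: sensitivity to discontinuations.** Suppose the 15% discontinuation rate applies on top of 46% and 26%, and those subjects count as failures. The rates become 0.46 × 0.85 = 0.391 and 0.26 × 0.85 = 0.221, a difference of 0.170 with mean 0.306. The same formula gives 0.446 at 60 per arm and 0.472 at 64.

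**Step 6: the 50% base and the boundary.** If 120 or 128 subjects were set against a final 204, the information fraction would be 120/204 = 0.59 or 128/204 = 0.63. The same spending function would then give about 0.035 or 0.037 instead of 0.031.

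**The case against.** The best defence is that 0.479 was not miscalculated. It is correct at half information for the 204-subject design, and half of 204 is a fair reading of the 50% wording. In the SAP, 240 × 0.85 = 204, so 120 *randomised* subjects would correspond to 102 evaluable and give the stated value. This explains where the number probably came from, but both documents count subjects who have *completed*, not subjects randomised. The route also fails for the protocol: 128 × 0.85 is about 109, which gives about 0.506.

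A continuity-corrected test at 60 per arm also comes close (0.473, or 0.480 by exact enumeration). No correction is stated for the CMH test; SAP Section 13.2.1 uses one only for the confidence interval of the difference. At 64 per arm it gives 0.506 (0.518 exact). At 102 per arm it gives two-stage power of 0.759, against the stated 80%.

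One point stands in part. Protocol Section 8.12.3 and SAP Sections 11.5 and 11.6 count discontinued subjects without closure as failures, and neither document says whether 46% and 26% already allow for that. If they do not, and such subjects are in the interim analysis set, the values fall slightly below 0.479 (Step 5). The direction of the error therefore depends on that assumption. The sentence carrying 0.479 applies 46% and 26% without dilution, and on those terms the probability is higher.

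It is also true that no boundary, alpha level, sample size or decision rule uses 0.479. That limits the consequence but does not make the figure right.

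**Conclusion.** The concern holds. The stated 0.479 describes a look at 102 subjects, while the documents specify 128 (protocol) or 120 (SAP). Under the stated 46% and 26%, two-sided 0.031 and equal allocation, it understates the chance of early success by 7 points at 120 and 10 points at 128. This assumes an uncorrected test of two proportions, completers split equally between arms, and closure rates that apply to the subjects analysed.

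The practical effect is modest. Type I error is not changed by this figure, and the 0.031 and 0.028 levels stand if the look is at half of the final analysed number. The more useful message is that the base for the 50% needs settling: SAP Section 11.1.1 expects 207 patients in the primary efficacy population, close to 204, and 120 or 128 is not half of that.

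**What to change.** State one interim count in both documents. Say whether it counts randomised, completed or evaluable subjects, and which total the 50% refers to. Then give the probability that goes with it at 46% versus 26%:

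- interim at 120 completed subjects: 0.55;
- interim at 128 completed subjects: 0.58;
- or keep 0.479 and define the interim at 102 evaluable subjects.

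Add a sentence saying whether the assumed rates already include discontinuations counted as failures; if they do not, recompute with the diluted rates.

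For the first two options, the probability changes in the protocol synopsis, Protocol Section 8.6 and SAP Section 9.1, and the interim count is aligned between the documents. The third instead changes the interim counts in the protocol synopsis, Protocol Section 3 and SAP Section 4. No additional data or clinical procedure is involved. If the look has already been taken, report the number actually analysed and the probability for that number.
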